### **C.12. Intervention Component – Home BP Monitoring [medium/level 1 and high/level 2 resource intensity]**

All patients randomized to the intervention arm who do not currently have a VA approved home BP monitor will receive one. All intervention patients will receive training in its use at their baseline study visit according to a protocol developed in our prior studies. If a patient must leave the study visit before receiving training or randomization must be revealed over the phone, the study team may either schedule a follow-up appointment for training or walk the patient through use of the home BP monitor over the phone. Patients will use BP monitors every other day to check their BP, using a defined protocol similar to the one in previous studies. We will request individuals to provide their BP values for at least the two weeks prior to the monthly intervention phone calls so that the interventionist [RN or PharmD] can comment on BP control. Patients will be reminded to record their blood pressures as part of the intervention telephone calls. Examinations of the agreement between self-reported and electronically stored blood pressure has generally been good, with one study of agreement indicating that 68% of reported home systolic BP measurements were identical to those stored electronically. In a previous study, we were able to maintain an 84% home BP monitor compliance rate over 24 months (instructions submitted separately to the Durham VAMC IRB). [Submitted for approval with this protocol]

Because this is a pragmatic clinical trial, it is expected that some patients may choose not to obtain a home BP monitor from the VA. Clinical judgment will be utilized in determining which home blood pressure readings will be recorded and utilized as part of study intervention.

### **C. 13. Intervention Component – Pharmacist-Directed Algorithmic Medication Management [high/level 2 resource intensity]**

Many patients require medication intensification to achieve targets for BP. Appropriate medication management requires accurate and timely information on the patient's current level of disease control, treatment adherence, evidence-based recommendations, and potential barriers to successful implementation. Patients who meet criteria for high/level 2 resource intensity disease management will receive medication management from a clinical pharmacist, who will be backed up by an MD ([name] or his appropriately licensed back-up/replacement who could be a mid-level provider). Pharmacists are authorized to make medication changes according to accepted treatment algorithms and based on their scope of practice. Via CPRS, the pharmacist will also communicate these changes to the patient's PCP. While pharmacists may collaborate with the patients' providers when clinically indicated, they do not have to rely on providers to make the changes. The goal of the medication component of the intervention is not to replace clinic based management, but rather to supplement it based on home BP readings in order to more efficiently implement interventions that may otherwise be left until the next provider appointment. The pharmacist will attempt to contact patients every month while they are in the high-intensity titration level of the intervention. At the pharmacist's discretion, patients may be asked to come to the Durham VAMC for an in-person meeting, however, most interactions will be conducted over the phone. During each encounter, the pharmacist will have information from both CPRS and the behavioral-telephone calls conducted as part of the intervention so information on such topics as patient medication and barriers to adherence can be available. During the initial encounter the pharmacist will assess the patient's medication adherence, review all BP related medications, discuss the purpose of each medication, and the appropriate administration of each medication. While not explicitly planned, the pharmacist (or appropriately licensed clinical backup) may discuss other medicines if he or she feels that this is needed to appropriately manage BP medication. At subsequent contacts the pharmacist will review any medication changes with the patients and update patients' medication lists. All calls will be indicated with a note in the Durham VAMC electronic health record.

For patients who require a change in their prescription, the pharmacist will communicate the change to the VA pharmacy and the patient's PCP using standard clinic procedures. At the next monthly telephone contact, the pharmacist will assess any new symptoms (e.g., hypotension). This will allow adequate time for the patient to obtain the medication and to get accustomed to the medication change. Any medication change that requires additional testing or follow-up (e.g., assessment of serum potassium, sodium and creatinine following the addition of an ACE-I or diuretic) will be ordered and followed-up. In cases where a medication change is made, a note will be generated for the patient's medical record and co-signed by the patient's PCP. This algorithm and methods of communication of changes to the PCP and follow-up of required labs has all been developed and tested in the HINTS study. If any significant adverse events occur, the pharmacist will consult with the patients' provider along with the study physician ([name] or his appropriately licensed back-up/replacement who could be a mid-level provider or other appropriate clinician) to take appropriate action and/or make further recommendations. Patients will also be provided with a toll-free number to call the pharmacist to report any adverse events or ask questions. All medication changes will be indicated with a note in the Durham VAMC electronic health record. Medications algorithms are being submitted separately to the Durham VAMC IRB. [approved by IRB on August 24, 2011]

Because this is a pragmatic clinical trial, it is expected that patients may not be able to be contacted or miss some portion of the scheduled telephone calls or other contacts with study personnel.

#### **C.13.a. Hypertension Medication Management**

We have previously developed a set of clinical rules, based on VA practice guidelines to facilitate telephone management of BP medications. Many of the clinical rules are based on the following treatment principles:

- a. Encourage use of diuretics as first-line agents, which have established effectiveness in reducing long-term morbidity and mortality.
- b. Select drug partners with favorable interactions, for example, diuretic and ACE inhibitor.
- c. Avoid drug partners with potential adverse interactions (e.g., ACE inhibitor and potassium-sparing diuretic (increases risk of hyperkalemia)).
- d. Avoid drug partners that do not have added efficacy (e.g., ACE inhibitors and angiotensin II receptor antagonists).

- e. In patients with additional diseases, select drugs that are appropriate for dual effects, for example, ACE inhibitor in a diabetic patient in an effort to preserve renal function.
- f. Avoid drugs that may aggravate other health problems (e.g., avoid calcium channel antagonists in patients with gastroesophageal reflux disease since these agents may lower pressure in the lower esophageal sphincter).
- g. Encourage appropriate intervals before assessing the impact of the drug (e.g., waiting one month for the full effect of hydrochlorothiazide as compared with several days for the full effect of calcium channel antagonists).
- h. Be aware of potential withdrawal syndromes (e.g., change from beta receptor antagonists or clonidine).

#### **C.14. Procedures for Assessing Immediate Patient Risks.**

During each scheduled encounter between a patient and study interventionist, immediate patient risks will be assessed via brief clinical questions asked by the interventionist. Emergent concerns will require referral to emergency care for immediate medical attention, usually by having the patient call 911. These include active chest pain, typical cardiac chest pain of duration > 10 minutes within the last 24 hours, dyspnea, SBP  $\geq$  220 mmHg, DBP  $\geq$  120 mmHg, SBP  $\leq$  90 with lightheadedness, heart rate  $\geq$  120, heart rate  $\leq$  50 with lightheadedness, new severe generalized or focal weakness, and altered mental status. In response to all other concerns not related to blood pressure the patient will be urged to contact his/her PCP. This same basic procedure was used during our recently completed Diabetes Group Visits Trial. Only one patient was referred for emergency care among over 600 patient-visits to that study. In addition, section C.19 outlines safety parameters for the primary outcome (BP).

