### **C.19. Safety Parameters for Primary Outcome**

Certain extreme BP values, both high and low, carry an urgent risk of major complication. As a result, if the most recent BP measurement is reported during a patient phone call, at a study data collection visit, or during other contact between study clinical staff and a patient is at one of these extremes, we will advise patients to take specific actions to minimize those risks. For SBP  $\geq$  180 mmHg or DBP  $\geq$  110mmHg, we will advise the patient to contact her/his triage nurse (or other similar position) within 24-48 hours. If a patient is advised to contact the triage nurse, a note will be placed in the patient's medical record. For participants that have moved care to a different VA facility (as described in section C.3.b) we will advise patient to go to the emergency room or urgent care facility but not put a note that requires PCP co-signature in their medical record (because it is not possible to require co-signatures of providers from another facility). This level corresponds to JNC 7

classification of Stage 3 hypertension and are the safety criteria currently used by our data safety monitoring board in TCYB and TEACH-DM. For SBP  $\geq$  210 mmHg or DBP  $\geq$  120 mmHg, or SBP  $\leq$  90 mmHg and/or DBP  $\leq$  40, we will advise the patient to seek immediate care. For all instances in which we recommend seeking immediate care, we will put a note that requires PCP co-signature in the patient's medical record. For participants that have moved care to a different VA facility (as described in section C.3.b) we will advise patient to go to the emergency room or urgent care facility but not put a note that requires PCP co-signature in their medical record (because it is not possible to require co-signatures of providers from another facility).

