#### **I.5. Procedures for Assessing Immediate Patient Risks.**

During each scheduled encounter between a patient and study interventionist, immediate patient risks will be assessed via brief clinical questions asked by the interventionist. Emergent concerns will require referral to emergency care for immediate medical attention, usually by having the patient call 911. These include active chest pain, typical cardiac chest pain of duration > 10 minutes within the last 24 hours, dyspnea, SBP ≥ 220

mmHg, DBP  $\geq$  120 mmHg, SBP  $\leq$  90 with lightheadedness, heart rate  $\geq$  120, heart rate  $\leq$  50 with lightheadedness, new severe generalized or focal weakness, and altered mental status. In response to all other concerns not related to blood pressure the patient will be urged to contact his/her PCP.

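### The urgent blood-pressure limits in C.14/I.5 and in C.19/I.3 differ, and nothing says whether they are one rule or two tiers

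*Protocol*

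**What the plan says.** Four sections of the protocol give blood-pressure limits for urgent action.

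- **C.14** applies to interventionist contacts: "During each scheduled encounter between a patient and study interventionist, immediate patient risks will be assessed". Its blood-pressure entries are "SBP $\geq$ 220 mmHg, DBP $\geq$ 120 mmHg, SBP $\leq$ 90 with lightheadedness", within a longer list of symptoms and heart-rate limits. The action is strong: "Emergent concerns will require referral to emergency care for immediate medical attention, usually by having the patient call 911". The section ends by noting that C.19 also gives safety parameters for blood pressure.
- **I.5** repeats the C.14 list, including "within the last 24 hours, dyspnea, SBP ≥ 220", but has no pointer to C.19.
- **C.19** applies when a reading is reported on a patient call, at a study visit, or in other contact with clinical staff. It has two levels. At SBP ≥180 or DBP ≥110 the patient is told to contact the triage nurse within 24–48 hours. At SBP ≥210, DBP ≥120, SBP ≤90 and/or DBP ≤40, the text is "we will advise the patient to seek immediate care", with a chart note that the primary care provider must co-sign.
- **I.3** repeats the C.19 values, but differs from C.19 in one action for patients who have moved to another facility (see the comparison below).

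**The concern.** C.14 and C.19 both govern the same event: a blood-pressure value reported on a scheduled intervention call. If their limits differ and their relation is not stated, staff must work out during the call which list applies and which action follows.

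The calls run from standardized scripts in the intervention software (C.10.a.2, C.15), so the limits need to be stated once and unambiguously. Table 3 and C.11 say that LPNs work under the direction of other clinicians and do not assess patients independently. They are not the staff who should have to interpret two lists. The low-pressure limits matter as well as the high ones, because the intervention aims to lower blood pressure and I.2 accepts that low values may be seen.

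What is at stake is consistent handling of potentially urgent readings, not the treatment comparison.

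**Working it through.** No sample-size, power or event figure is involved, so the check is a reading-by-reading comparison of the two lists.

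| Reading | C.14 / I.5 | C.19 / I.3 |
|---|---|---|
| SBP ≥220 | Emergency referral, usually 911 | Advice to seek immediate care |
| SBP 210–219 | Not listed | Advice to seek immediate care |
| DBP ≥120 | Emergency referral, usually 911 | Advice to seek immediate care |
| SBP ≤90 with lightheadedness | Emergency referral, usually 911 | Advice to seek immediate care |
| SBP ≤90 without lightheadedness | Not listed | Advice to seek immediate care |
| DBP ≤40 with SBP >90 | Not listed | Advice to seek immediate care |

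(SBP 210–219 and the last two rows assume that no other criterion in the C.14 list is met.)

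Four things follow.

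1. **Overlap of setting.** C.14 covers every scheduled interventionist contact and C.19 covers any patient call, so both apply on an intervention call.
2. **Nesting.** Every blood-pressure value that is emergent in C.14 also meets C.19: ≥220 lies within ≥210, ≤90 with a symptom lies within ≤90, and the upper diastolic limit is the same. The reverse is not true; three kinds of reading meet C.19 only.
3. **No stated relation.** C.14 presents C.19 as additional but does not say that its own list is a higher tier or which action prevails on overlap. C.19 defines its own two levels and mentions no third level at 220. I.5 has no cross-reference. The documentation duty also differs: C.19 and I.3 require a co-signed note (with an exception for patients who moved facility), while C.14 and I.5 mention none.
4. **A direct conflict nearby.** For patients who have moved to another VA facility, at SBP ≥180 or DBP ≥110, C.19 sends the patient to an emergency room or urgent care facility, whereas I.3 has the patient contact the triage nurse. Here the same reading gets two different instructions. It suggests that the duplicated sections were not kept in step.

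**Frequency.** The documents do not say how often these readings occur. C.14 reports one emergency referral in more than 600 patient-visits of an earlier trial under the same basic procedure, that is, under 1/600 ≈ 0.17% of visits. That figure covers all emergency causes in another setting, so it supports rare and no more.

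**The case against.** The best defence is that the lists are two levels: C.14 a narrow 911 screen, C.19 a wider instruction to seek immediate care. Much of this stands. The C.14 list is introduced as illustrative rather than complete. Its fallback leaves blood-pressure concerns out: "In response to all other concerns not related to blood pressure the patient will be urged to contact his/her PCP". It then adds C.19. A careful reader of both sections would apply C.19 to SBP 210–219, to symptom-free SBP ≤90 and to DBP ≤40, and would reach one action. The shared limit of DBP ≥120 fits separate tiers poorly, but it does not exclude them, since two levels can coincide at one value.

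Four stronger readings are tempting, and the documents do not support them.

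- **Opposed orders.** A reader might infer that one reading on one call receives two opposed orders from the two lists. It does not. The values are nested, and C.14 gives no contrary instruction where only C.19 is met.
- **Escalation.** A reader might infer that the automatic escalation rule in C.9.c becomes ambiguous. It does not. C.9.c cites C.19 alone, all three kinds of reading are in C.19, and SBP 210–219 already exceeds C.19's lower limit of 180.
- **Equal exposure of the arms.** Control calls are LPN booster calls, and C.11 says the LPN does not ask about home measurements. A patient may still volunteer a value, but exposure lies mainly in the intervention arm.
- **Scripts.** A reader might assume that the call scripts carry the same discrepancy. They were submitted separately and are not in the document, so this cannot be judged.

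The tiers that the defence needs are nowhere stated, and I.5 lacks even the pointer that makes the reading possible.

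**Conclusion.** The point holds as an unreconciled set of limits. Four sections carry unequal values for urgent action, three kinds of reading appear in one pair of sections and not in the other, and the values common to both pairs have differently worded actions. Someone working from C.14 or I.5 alone could miss an immediate-care trigger. The facility-transfer instruction is a plain contradiction between C.19 and I.3.

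The size is modest. Such readings should be rare and occur mainly on intervention-arm calls. Randomisation, the primary outcome, its analysis and the titration rules are untouched. The correction is still worth making, because it concerns patient safety and costs little. The conclusion rests only on the protocol text and the assumption that staff follow it as written. It takes no position on which values or actions are clinically right.

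**What to change.** Reconcile C.14, C.19, I.3 and I.5 in one of two ways:

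- a single list of blood-pressure values, each with its action and documentation duty, to which the other sections refer; or
- explicitly labelled tiers, with a sentence saying which action prevails when a reading meets more than one.

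In either case:

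- say whether symptoms are part of the low-pressure criterion, and whether a low diastolic limit belongs in the interventionist screen;
- give one instruction for patients who have changed facility;
- add to I.5 the cross-reference that C.14 has;
- check that the call scripts match the reconciled text.

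The study physicians must set the values and actions. The cost is an amendment to protocol wording and, if the check shows a need, to the scripts. Design, sample size and analysis do not change.

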#### **C.15. Measuring Components and Fidelity of the Intervention.**

At each intervention encounter, the interventionists (i.e. nurse or pharmacist) will review a checklist of issues pertinent to that particular patient. The checklist will be maintained in the intervention database, which the interventionist will use while s/he is conducting intervention calls. The database will facilitate ascertainment of compliance with this intervention.

All telephone calls initiated by the interventionist will be conducted while s/he is logged on to the intervention database created for the study. This will record the number and duration of calls and the type of intervention components delivered for each patient that will be used for cost analyses. The database will also contain a standardized script. In the intervention software, the interventionists will maintain a log for calls initiated by patients and calls to providers. Further, a log of all consultations by study interventionists/clinicians on patient clinical issues will be maintained in the intervention software. This includes any contacts with a patient's PCP. All pharmacist-made medication changes will be recorded in the intervention software (in addition to CPRS). The project coordinator will review all logs weekly to assure that the components that were due at the scheduled call were in fact recorded as delivered. Drs. [name] and [name] (or his appropriately licensed back-up/replacement) will meet with the interventionists approximately monthly to discuss any possible problems with the scheduled delivery of the intervention. A member of the unblinded study team will listen to approximately 1 phone call approximately every 2 weeks to ensure that what is being recorded in the databases is actually being covered on the calls. The process may become less frequent if consistent quality is observed. In addition, more phone calls may be listened to if necessary to ensure quality.

#### **C.16. Control Arm**

Patients in the control arm will receive the booster level resource intensity LPN phone calls that will also be received by patients in the intervention arm whose hypertension comes into control (described in section C.11). Control patients will be contacted at 6, 12, and 18 months after randomization in order to come to an in-person study visit to complete the same outcome measures as the intervention group.

This process differs from usual care and emulates phone calls based on those that have been shown to be effective at improving blood pressure control and patient medication adherence in both clinical trial and implementation settings. Phone calls used in the V-STITCH study were not-tailored based on the patient's stage of change for a specific concern (e.g. all smokers received the same information on smoking regardless of how ready they were to quit smoking). Further, the calls only occurred every two months. Despite these

limitations, receiving the phone calls was associated with a significant increase in hypertension control compared to not receiving the phone calls. In addition to this trial evidence, the implementation of bi-monthly calls using scripts provided by [name] in a purely quality improvement project was associated with significant improvement in patient adherence to hypertension medication. As a result, we are proposing a control arm that would be expected to lead to modestly reduced systolic BP and do it at a low cost per patient.

51

### **C.17. Evaluation of the Intervention to Inform Future Translation into Practice**

All telephone calls initiated by the study interventionists will be conducted while they are using the intervention software, which will record the number and duration of calls and the type of intervention components delivered for each patient. The schedule for telephone calls between interventionists and patients will be closely monitored and intervention sessions will be randomly reviewed to ensure intervention fidelity.

Measuring process data is an important component of any well-designed intervention trial, with results used to help understand why an intervention was or was not effective. The process research proposed here is designed with a focus on enhancing the readiness of the interventions for translation. Successful translation into real-world settings has three components: 1) adoption of these interventions by practice settings outside of the research context, 2) successful implementation of the interventions in these settings, and 3) effective use of the interventions by the populations accessed or served through these settings. Greenhalgh et al describe the diffusion of innovations into service organizations as conditioned by characteristics of: the innovation (in this case, the interventions), individual adopters and their service systems, the sources of innovation and mechanisms of diffusion and dissemination, and the larger inter-organizational context. Changing service system readiness for adoption and implementation of innovations is clearly beyond the scope of this project. However, making the intervention more ready for effective adoption, implementation, and use in practice settings is a natural extension of this work that helps fulfill the mandate to promote translation.

Reasons for increased likelihood that the intervention will be ready for effective translation into practice include: 1) the behavioral modules are standardized, consistent and tailored to patients' needs. Thus, the modules are only activated for those with problems (e.g., side effects) and when activated, the modules are tailored to the patient's current stage of change. As a result, each phone call encounter is less than 20 minutes. 2) The medication algorithm for diabetes, hypertension, and lipids has been developed. In addition, the algorithm focuses on generic and low cost medications. 3) The intervention software package is extremely adaptable and can function in a paper and electronic medical record environment. The software allows the integration of patient, medical records, and provider information and can be easily changed to update medication or guidelines changes. 4) The various components of the material have been tested in over 2500 patients in 6 diverse clinics.

